**AMENDMENT INCORPORATES (check all that apply):**

- Editorial, administrative changes
- Scientific changes
- Therapy changes
- Eligibility Changes

**AMENDMENT RATIONALE AND SUMMARY:**

The purpose of this amendment is to update secondary and exploratory endpoints and make administrative changes. The sponsor has asked for these changes.

The following changes have been made to the protocol:

- Section 1.1 Updated target population and study participation duration
- Section 2.0 Updated secondary and exploratory endpoints
- Section 4.1 Updated study schema, changed study participation duration, updated timepoints for patient and provider satisfaction surveys
- Section 4.2 Updated study duration, enrollment period, and accrual goal
- Section 4.3 Updated unattended alerts escalation process, and outcome surveys timepoints
- Section 5.1 Updated time and event table to reflect the change in the study participation duration and updated survey frequency
- Section 7.1 Clarified primary objective
- Section 7.2 Updated sample size and accrual duration
- Section 7.3 Updated post-baseline assessment time point under supplemental analysis to remove the time points after 6 months.
- Section 7.5 Updated language on AE and SAE collection and reporting and updated unattended alerts escalation process

***THE ATTACHED VERSION DATED APRIL 19, 2022 INCORPORATES THE ABOVE  
REVISIONS***

## 1.0 BACKGROUND AND RATIONALE

### 1.1 Study Synopsis

This single site study is being conducted to evaluate the feasibility and acceptability of monitoring lung cancer patients' disease- and therapy-related symptoms remotely with electronic patient-reported outcome (ePRO) surveys. Up to 50 patients undergoing treatment and/or surveillance for new or existing diagnoses of lung cancer at the University of North Carolina's Lineberger Comprehensive Cancer Center will be prospectively enrolled to the use of the mobile medical application Moovcare® for 6 months. Moovcare® automatically delivers ePRO surveys on common symptoms experienced by lung cancer patients. Results are stored in a secure web-based portal for provider review. Concerning survey responses are reported to a designated provider via an email alert.

This study will evaluate and report on: patient adherence with surveys, patient and provider satisfaction with Moovcare®, quality of life, and survival during the study period.

### 1.2 Background

In the United States, lung cancer was the third most commonly diagnosed cancer (>200,000 cases) and the leading cause of cancer death (>140,000 fatalities) in 2019. While the majority of lung cancer patients are at an advanced stage at presentation and survival is still less than 20% at 5 years, increasing numbers of patients are living longer due to advances in chemotherapy and immunotherapy regimens. Lung cancer patients are highly symptomatic due to the tumor itself and the side effects of multimodal therapy. Therefore, strategies for systematic outpatient symptom monitoring that lead to earlier clinician management before symptoms become severe and lead to emergency department visits, hospitalizations, or other complications are anticipated to be clinically meaningful in this group.

Electronic patient-reported outcome (ePRO) surveys can be used to monitor symptoms related to disease and treatment remotely in ambulatory patients. ePRO monitoring systems automatically deliver surveys that capture symptoms directly from patients and alert providers in real-time to concerning responses above predetermined symptom severity thresholds. ePRO monitoring has been shown to result in improvement of routine clinical care in the oncology population. In a large randomized controlled trial of advanced cancer patients, ePRO monitoring was associated with reduced emergency department (ED) visits and hospital readmissions, improved quality of life (QOL) and patient satisfaction, and increased overall survival, findings supported by other studies.

Moovcare® is a web-mediated ePRO survey delivery and monitoring system designed for the detection of recurrent lung cancer. Patients are automatically

reminded through emails to complete weekly surveys on symptoms common to lung cancer patients. Providers are notified for concerning changes in symptoms based on a previously validated algorithm predictive of lung cancer recurrence. In prior studies, lung cancer recurrence in patients with advanced lung cancer was detected earlier and survival was improved in patients using Moovcare®.

### **1.3 Purpose and Rationale**

The purpose of this study is to demonstrate the feasibility and acceptability of using Moovcare® to monitor symptoms related to complications of treatment (surgery, radiotherapy, and/or chemotherapy) and disease recurrence in American lung cancer patients as well as to provide preliminary data to inform future controlled studies on the association of ePRO monitoring with clinical and quality of life outcomes.

The study of the implementation of mobile health information technology (HIT), such as Moovcare®, in diverse patient populations and settings is important to identify and solve barriers to uptake. This study will endeavor to show feasibility of ePRO HIT in patients receiving care at the University of North Carolina (UNC), a large public, academic hospital setting. In a separate UNC study looking at the feasibility and impact of ePRO monitoring for the initial 90 days after discharge from thoracic surgery (including lung resection for cancer), initial study experience suggests ePRO use is likely to be feasible in other patients with intrathoracic pathology including lung cancer patients. Evaluating compliance with longitudinal ePRO monitoring throughout the treatment and surveillance periods of lung cancer patients will allow protocols for use in multidisciplinary care to be developed.

## **2.0 STUDY OBJECTIVES AND ENDPOINTS**

### **2.1 Primary Objectives**

- 2.1.1** The primary objective of the study is to evaluate the feasibility of self-reporting symptoms by lung cancer patients using Moovcare®. Feasibility will be defined as the mean of assigned weekly ePRO surveys completed per patient.
- 2.1.2** The primary endpoint will be:
  1. ePRO survey completion rate: the mean percentage of surveys completed per patient by 6 months or coming off study per protocol if sooner.

### **2.2 Secondary Objectives**

The secondary objectives of the study will be to evaluate the acceptability of Moovcare® (through patient and provider satisfaction surveys) and estimate the overall survival and change in the quality of life in patients using Moovcare®.

**2.2.1 Secondary Endpoints will be:**

1. Percentage of patients surveyed at 6 months on study satisfied with care team communication.
2. Health-related quality of life (HRQOL): change in comprehensive EORTC-QLQ30 and LC13 survey score from baseline at 6 months.
3. Overall Survival (from time of enrollment).
4. Percentage of surveys completed at each weekly delivery time point

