#### Outcome Surveys

At enrollment, all participants will be trained by the study coordinator how to use the UNC REDCap online system to complete outcomes surveys for the trial. The outcomes surveys will be completed by all participants at baseline; HRQOL will be reassessed at months 3, 6/off-study (+/- 4 weeks each) and patient satisfaction at 6 months/off-study (+/-4 weeks). Participants will be given a choice to complete from home electronically, or if necessary, in clinic at otherwise scheduled routine follow-up visits which occur at least every 3 months or via phone call (with the study coordinator entering the data after participant paper completion into REDCap). For home electronic completion, the outcomes surveys will be sent when due by email via REDCap. The REDCap will send automatic reminders for incomplete surveys. If the patient does not self-complete this information, the study coordinator also has the option to call or email them to collect the information and then enter it into REDCap. If the patient goes off study prior to week 26, the study coordinator will contact the patient as soon as possible to get the off-study surveys completed.

The patient outcomes surveys include:

- **Participant Demographics Form:** This form asks participants about their baseline information including full name and date of birth and will be administered at the time of enrollment.
- **Quality of Life Questionnaires:** Health-related quality of life will be

assessed by items from the *European Organisation for Research and Treatment of Cancer* Quality of Life Questionnaire Comprehensive 30 (EORTC-QLQ-C30) and Quality of Life Questionnaire Lung Cancer 13 module (EORTC-QLQ-LC13), which will be administered to each patient participant at baseline, months 3, 6/off- study (+/- 4 weeks each). The EORTC is a well-established and frequently used questionnaire that includes a 5-item physical functioning domain, individual symptom items including symptoms specific to lung cancer patients, and a composite quality of life score.

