- **Patient Satisfaction Survey:** The patient satisfaction survey will be administered to each participant at baseline and 6 months of participation (+/- 4 weeks). The satisfaction questions are from the Consumer Assessment of Healthcare Providers and Systems (CAHPS) survey system, which is maintained by the Agency for Healthcare Research and Quality (AHRQ), to support and promote the assessment of consumers' experiences with health care, and from the "Patient-Centered Communication in Cancer Care" short form and validated instrument (PCC-CA-6). No total score is calculated, but individual items will be summarized and reported.

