#### Off-Study Timing and Procedures

Participants are asked to remain on the study completing surveys for 6 months (26 weekly ePROs), or until they go off-study prior to that time. An "Off-study form" requiring information to be abstracted from the participant's medical record will be completed by the study coordinator when the participant goes off study (+ 4-week window for form completion). Consultation with MTOP physician or nurse may be necessary for clarifications of some of the questions in

this form. For example, this form includes information about reasons and timing for the reasons for going off-study. In addition, the final chart abstraction form will also be completed (see above) when going off study. In addition, if a patient goes off study early for any reason other than death, the coordinator will attempt to contact the patient to complete the final Outcomes Questionnaires (including: “Patient Quality of Life” and “Patient Satisfaction”) as soon as possible.

Some of the reasons for patients going off-study include:

- Completion of 6 months (26 weeks) of participation
- Initiation of hospice
- Death
- Moved to a different practice for lung cancer care
- Voluntary disenrollment
- Lost to follow-up
- Removal by principal investigator

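### The 6-month satisfaction percentage, as worded, leaves out patients who formally go off study early, although the plan seeks a final satisfaction survey from them

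*Combined protocol and SAP*

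**What the plan says.** The endpoint is "Percentage of patients surveyed at 6 months on study satisfied with care team communication" (section 2.2.1). It serves the objective in section 2.2 to "evaluate the acceptability of Moovcare® (through patient and provider satisfaction surveys"). Section 7.3 lists patient satisfaction at 6 months among the primary data analyses and promises descriptive statistics for the satisfaction scores. It gives no denominator and no rule for missing surveys.

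The conduct sections go further. Under Outcome Surveys, section 4.3 schedules "patient satisfaction at 6 months/off-study (+/-4 weeks"), and for anyone leaving before week 26 it says that "the study coordinator will contact the patient as soon as possible to get the off-study surveys completed". Under Off-Study Timing and Procedures, for early exits other than death, "the coordinator will attempt to contact the patient to complete the final Outcomes Questionnaires", and patient satisfaction is named among these. Section 5.1 uses a single Month 6/Off-study column. The description of the instrument in section 4.3 has only the narrower timing: the survey "will be administered to each participant at baseline and 6 months of participation (+/- 4 weeks").

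**The concern.** Acceptability is judged partly through this percentage, and some exits can be related to acceptability. Section 4.3 lists voluntary disenrollment as a reason for going off study, and section 4.5 removes patients whom remote monitoring distresses. If the denominator is limited to patients still on study at 6 months, the result depends on having stayed, and staying may itself go with being satisfied. The surveys sought from early leavers then have no stated role in the endpoint.

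The other way to read the plan has its own problem. If off-study forms are pooled into Month 6, a form completed in an early week is reported as a 6-month result. Two analysts could follow the plan in good faith and publish different percentages from the same data.

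**Working it through.** **Step 1. Set the places side by side.**

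| Place | Timing of the satisfaction survey | Early leavers |
|---|---|---|
| 2.2.1, endpoint 1 | 6 months, on study | not mentioned |
| 7.3 | 6 months | not mentioned |
| 4.3, Patient Satisfaction Survey | baseline and 6 months | not mentioned |
| 4.3, Outcome Surveys | 6 months or off-study | contacted if leaving before week 26 |
| 4.3, Off-Study Timing and Procedures | at early exit | contact attempted, deaths excepted |
| 5.1, list and schedule | Month 6/off-study | share the Month 6 slot |

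The first three rows define or analyse satisfaction at 6 months only. The last three also seek it at early exit. No unredacted text assigns the off-study survey to the endpoint. By contrast, the primary endpoint (section 2.1) is "the mean percentage of surveys completed per patient by 6 months or coming off study per protocol if sooner", so the plan covers early leavers explicitly where it means to. For quality of life, section 7.3 gives a carry-forward sensitivity analysis and a rule for deaths. Satisfaction has neither.

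**Step 2. Illustrate the possible size.** The plan states no satisfaction rate, drop-out rate or precision for this endpoint, so there is no figure to reproduce. The only input from the documents is the target of 50 patients (section 7.2). All rates below are assumptions.

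- Completers-only percentage = satisfied at month 6 / surveyed at month 6.
- Final-survey percentage = (satisfied at month 6 + satisfied at off-study) / (surveyed at month 6 + surveyed at off-study).

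Assume that about 90% of completers and 40% of leavers are satisfied, and that every leaver is alive and responds:

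| Leave early | Completers only | Final survey | Gap (points) |
|---|---|---|---|
| 5 of 50 | 40/45 = 88.9% | (40+2)/50 = 84.0% | 4.9 |
| 10 of 50 | 36/40 = 90.0% | (36+4)/50 = 80.0% | 10.0 |
| 15 of 50 | 32/35 = 91.4% | (32+6)/50 = 76.0% | 15.4 |
| 20 of 50 | 27/30 = 90.0% | (27+8)/50 = 70.0% | 20.0 |

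**Step 3. Vary the assumptions, with 10 of 50 leaving.**

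- 36/40 completers satisfied, 6 of 10 leavers satisfied: 42/50 = 84.0%, gap 6.0 points.
- 36/40 completers satisfied, 8 of 10 leavers satisfied: 44/50 = 88.0%, gap 2.0 points.
- 80% satisfied in both groups: 32/40 = 80.0% against (32+8)/50 = 80.0%, gap zero.
- 32/40 completers satisfied, all 10 leavers satisfied: 42/50 = 84.0%, so the completers-only figure is 4.0 points too low.
- 36/40 completers satisfied, only 5 leavers respond and 2 of them are satisfied: 38/45 = 84.4%. Counting the 5 surviving non-responders as not satisfied gives a lower bound of 38/50 = 76.0%.
- 36/40 completers satisfied, no leaver responds: the bounds over all 50 run from 36/50 = 72.0% to (36+10)/50 = 92.0%.

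**Step 4. Compare with sampling error.** For 36/40 the exact (Clopper-Pearson) 95% interval is 76.3% to 97.2%. A 10-point gap falls inside it. The interval describes chance variation among completers, however, and does not allow for selection by leaving.

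**The case against.** The best defence is that nothing in the plan expressly excludes off-study forms. The phrase in 2.2.1 can be read as a visit label. Section 5.1 has one Month 6/Off-study column, and section 4.3 counts completing 26 weeks as itself a reason for going off study. Section 7.3 promises descriptive statistics for satisfaction without restricting them in time, and further exploratory material is redacted. This stands to the extent that exclusion cannot be called the plan's declared intention. It does not settle the denominator, and it leads to the mislabelling problem.

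Three stronger readings are tempting, and the documents do not support them.

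- *Everyone who stops using Moovcare drops out of the result.* Ceasing to answer weekly surveys is not a listed off-study reason in 4.3 or a removal criterion in 4.5, and section 8.4.3 does not treat non-adherence as a deviation. Such a patient, unless disenrolled or lost to follow-up, is still due the month-6 survey.
- *The percentage is necessarily too high, or could never show low acceptability.* Dissatisfied patients who stay are counted. The endpoint concerns communication with the care team, not the application, and leaving the study need not mean dissatisfaction with that. Hospice, death and a move to another practice also end participation.
- *The plan will hold a survey from every early leaver.* It promises an attempt, and deaths are excepted.

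It is also fair that early leaving is visible elsewhere: in the off-study form, the primary endpoint and the weekly completion percentages. Those sources show who left and when, but not how satisfied they were.

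**Conclusion.** The point holds in a limited form. Taken as worded, endpoint 1 and section 7.3 leave out patients who formally go off study early, although sections 4.3 and 5.1 seek their satisfaction surveys. The percentage may therefore understate dissatisfaction. Understatement is the likelier direction, because some exits can reflect how patients found the monitoring, but the documents fix neither direction nor size. In the assumed scenarios the completers-only figure ranges from 4 points too low, through no difference, to 20 points too high.

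The consequence is modest. The endpoint is secondary and descriptive, and no threshold, test or sample size depends on it. It is still worth correcting, because section 7.1 includes acceptability in the primary objective and section 7.3 places satisfaction in the primary data analysis.

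**What to change.** 1. Reconcile 2.2.1, 7.3 and the Patient Satisfaction Survey description in 4.3 with Outcome Surveys and Off-Study Timing and Procedures in 4.3 and with 5.1, so that all give the same timing and denominator.
2. Keep the 6-month on-study percentage and label it as completers only. Do not pool off-study forms into it. State how an off-study form completed inside the 4-week window around month 6 is classified.
3. Add a companion percentage in 2.2.1 and 7.3 that uses each enrolled patient's final satisfaction survey (month 6, or off-study if earlier) and excludes patients who die before the survey.
4. Report the numbers enrolled, surveyed at month 6, surveyed at off-study (with week and reason), dead before the survey, and otherwise missing.
5. Show a lower bound for the companion percentage that counts surviving non-responders as not satisfied.

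The cost is a few sentences and a little more tabulation, with no new visit or instrument, since the surveys and the off-study reason and timing are already sought. The drawbacks are that off-study forms come at mixed times, some leavers will not respond, and the companion figure may be slightly less favourable.

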**2.2.2 Exploratory endpoints will be:**

1. [REDACTED]

## 3.0 PATIENT ELIGIBILITY

### 3.1 Inclusion Criteria

Patients participating in the study must meet the following inclusion criteria at baseline:

- 3.1.1 18 years or older
- 3.1.2 Diagnosis of lung cancer (any histology, any stage) undergoing outpatient treatment and/or surveillance/monitoring at UNC.

*This may include stage I and II patients who have completed lung resection and/or are undergoing radiation, stage II and III patients receiving neoadjuvant, adjuvant, or definitive chemotherapy, stage IV patients undergoing active therapy or monitoring, patients undergoing surveillance for treated or untreated stage I-III lung cancer, and both limited and extensive small cell lung cancer. The study team will request confirmation of the lung cancer diagnosis from the managing clinician. Patients can be enrolled at any point in their lung cancer treatment trajectory (i.e., not just at initiation of first-line treatment) after a diagnosis of lung cancer has been assigned by the treating clinician. This may include patients assigned a diagnosis of lung cancer without a tissue diagnosis.*

- 3.1.3 Speaks and understands English
- 3.1.4 Reliable access to the internet and email
- 3.1.5 Access to a mobile phone (or device that can receive text messages for registration)

### 3.2 Exclusion Criteria

[figure not shown]
All participants meeting any of the following exclusion criteria at baseline will be excluded from study participation:

- 3.2.1 Dementia, altered mental status, or any psychiatric condition that would prohibit the understanding or rendering of informed consent or completing study procedures
- 3.2.2 Current participation in other PRO monitoring trials
- 3.3.3 Inability to read and speak English
- 3.3.4 Current incarceration

## 4.0 Study plan

### 4.1 Schema

**Figure 1: Study Scheme**

This is a single site nonrandomized feasibility study of approximately 50 participants on treatment and/or surveillance for new or existing diagnoses of lung cancer who will be assigned to a single-arm involving monitoring of their patient-reported outcomes using a mobile medical application. The study population will include patients with a diagnosis of lung cancer undergoing outpatient treatment or

surveillance at UNC. Patients will be recruited from the Multidisciplinary Thoracic Oncology Program (MTOP) clinics at UNC over 10-12 months and undergo ePRO monitoring for 6 months or until criteria for coming off study are met, whichever comes first. Study procedures include monitoring of patient symptoms using automated weekly PRO surveys delivered by Moovcare® and assessment of outcomes including quality of life at baseline and 3-month intervals, as well as patient satisfaction at 6 months using the UNC REDCap electronic survey delivery software platform. Other clinical outcomes including health care utilization, recurrence, and survival will be abstracted at any time after enrollment from the medical record into the UNC REDCap database. Provider satisfaction will be assessed via electronic survey after the study has been open to enrollment for at least 6 months.

#### 4.2 Duration of Study

This study will last for approximately 2 years. Training of providers will take place prior to enrollment starts. Approximately 50 participants will be enrolled over 1 year. Each participants' participation in the study will last up to 6 months or until the patient comes off-study due to transition to hospice, death, or withdrawal from the study. Study analysis of participant data will take place throughout the study duration and at the conclusion.

#### 4.3 Study Details

##### Overview

The study involves two types of repeating surveys: weekly PRO surveys delivered by e-mail via Moovcare® and periodic outcomes surveys delivered by e-mail via the UNC REDCap platform, a secure web-based server, or collected on paper in the clinic. PRO responses are managed by providers through a combination of reports graphically displaying responses over time and e-mail alerts about concerning levels or combinations of symptoms. Provider response to ePRO reports and alerts may lead to earlier or different management than routine clinical care and so potentially impact health care utilization and clinical outcomes. For all surveys (Moovcare® PRO and REDCap outcome surveys), participants' caregivers (family, friends) may assist with completion in any way the participant chooses. The study coordinator may also provide technical assistance.

